### 6.2. Background Characteristics

#### 6.2.1. Subject Disposition

The number and percentage of subjects in the following categories will be summarized by vaccination group as defined in [Section 6.1](#) based on Randomization Set:

- Randomization Set
- Full Analysis Set
- Immunogenicity Subset
- Per-protocol (PP) Immunogenicity Subset

- mITT Set
- mITT1 Set
- Per-protocol (PP) Set for Efficacy
- Solicited Safety Set
- Safety Set

The percentage will be based on subjects in that vaccination group within the Randomization Set (as randomized), except the Solicited Safety Set and Safety Set for which the percentages will be based on the vaccination group in the Safety Set (as treated).

The number of subjects in the following categories will be summarized based on subjects screened:

- Number of subjects screened
- Number and percentage of screen failure subjects and the reason for screen failure

The percentage of subjects who screen failed will be based on the number of subjects screened. The reason for screen failure will be based on the number of subjects who screen failed.

The number and percentage of subjects in each of the following disposition categories will be summarized by vaccination group based on the Randomization Set:

- Randomized by site
- Received each dose of IP
- Prematurely discontinued before receiving the second dose of IP and the reason for discontinuation
- Completed study
- Prematurely discontinued the study and the reason for discontinuation

A subject disposition listing will be provided, including informed consent, subjects who completed the study injection schedule, subjects who completed study, subjects who discontinued from study vaccine or who discontinued from participation in the study, with reasons for discontinuation. A separate listing will be provided for screen failure subjects with reasons for screen failure.

A subject who completed 12 months of follow up after the last injection received is considered to have completed the study.

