## 9.6. Appendix F Schedule of Assessments (Part 1B, Open-label Observational Phase for Subjects Who Previously Received Placebo)

	Visit Number	7	8	9	10	11
	Type of Visit	C	C	C	SC 	C
Study Visit Day	(~D209/ Participant Decision Visit) OL-D1	OL-D29	OL-D57 	OL-D113	OL-D178 	
Window Allowance (Days)	-56/+56 	-3/+7	±14	±3	±14	
Days Since Most Recent Injection	0	28	28	84	84	149
Informed consent form	These assessments are already performed as part of the regular D209 Visit.		X			X
Blood for vaccine immunogenicity			X			
Nasopharyngeal or nasal swab sample for SARS-CoV- 2 			X			
Physical examination including vital signs 						X
Pregnancy testing						
Study injection (including 30-minute postdosing observation period)	X	X				
Informed consent for BD				X 		
Recording of MAAEs and concomitant medications relevant to or for the treatment of the MAAE 	X	X	X	X	X	X
Recording of SAEs and concomitant medications relevant to or for the treatment of the SAE 	X	X	X	X	X	X

	Visit Number	7	8	9	10	11
Type of Visit	C	C	C	SC 	C	
Study Visit Day	(~D209/ Participant Decision Visit) OL-D1	OL-D29	OL-D57 	OL-D113	OL-D178 	
Window Allowance (Days)	-56/+56 	-3/+7	±14	±3	±14	
Days Since Most Recent Injection	0	28	28	84	149	
Recording of AESI	X	X	X	X	X	
Recording of concomitant medications and nonstudy vaccinations 	X	X	X	X	X	
Surveillance for COVID-19/ Unscheduled visit	visit  /	X	X	X	X	
Study completion (for Part 1B)					X	

Abbreviations: AE = adverse event; AESI = adverse event of special interest; C = clinic visit; COVID-19 = coronavirus disease 2019; D = Day; M = month; MAAE = medically attended AE; NP = nasopharyngeal; OL = open-label; PCR = polymerase chain reaction; RT-PCR = reverse transcriptase polymerase chain reaction; SAE = serious adverse event; SARS-CoV-2 = Severe Acute Respiratory Syndrome coronavirus 2; SC = safety (telephone) call.

1. The Participant Decision Visit may be performed over multiple visits. Once the Participant Decision Visit has been initiated, all assessments must be completed within a 7-day period.
2. After the OL-D57 visit, Part 1B participants who choose to receive BD will have one additional safety call at OL-D113 prior to entering Part 1C-1..

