Section 7.1.6. In addition, the study site may collect an additional NP or nasal sample for SARS-CoV-2 testing to be able to render appropriate medical care for the study participant as determined by local standards of care. Additionally, clinical information will be carefully collected to evaluate the severity of the clinical case.

7. During OL-D57, all participants will be given the option to receive a BD. Participants will choose whether to receive the BD or not and sign the consent form. Those who decline BD will continue with Part 1B. Those who choose to receive a BD will have one safety call prior to entering Part 1C-1.
8. All participants in Part 1B who choose to receive BD will have one additional safety call at OL-D113 prior to entering Part 1C-1.
9. OL-D178 is only for those who decline BD. Participants who choose to receive a BD will follow Part 1C-1 SoA after the OL D113 safety call. The BD-D1 has a window of 1 month, thus, can be scheduled at least 5 months after the second dose, and participants will need to complete the OL-D113 safety call.

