### **3.2.4. Exploratory Endpoints**

The exploratory endpoints are the following:

- The GM values of SARS-CoV-2 S2P specific bAb on BD-Day 1, BD-Day 29 (1 month after BD), BD-Day 181 (6 months after BD), and BD-Day 361 (1 year after BD)
- The GM values of SARS-CoV-2-specific nAb on BD-Day 1, BD-Day 29 (1 month after BD), BD-Day 181 (6 months after BD), and BD Day 361 (1 year after BD)
- The incidence of SARS-CoV-2 infection (symptomatic or asymptomatic infection) counted starting 14 days after BD of mRNA-1273
- To evaluate the incidence of asymptomatic SARS-CoV-2 infection after vaccination with mRNA-1273 measured by RT-PCR and/or bAb levels against SARS-CoV-2 nucleocapsid protein (by Roche Elecsys) counted starting 14 days after BD in participants with negative SARS-CoV-2 at baseline or prebooster
- The incidence of the first occurrence of symptomatic COVID-19 starting 14 days after BD of mRNA-1273

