### 6.2. Background Characteristics

#### 6.2.1. Subject Disposition

The number and percentage of subjects in the following categories will be summarized by vaccination group as defined in [Section 6.1](#) based on specific analysis datasets for each part separately:

- Full Analysis Set
- Immunogenicity Subset

- Per-protocol (PP) Immunogenicity Subset
- Per-protocol (PP) Immunogenicity Subset - Pre-booster SARS-CoV-2 Negative (Part 1C-1 only)
- Per-protocol (PP) Immunogenicity Subset - Baseline SARS-CoV-2 Positive (Part 2 and Part 3)
- mITT1 Set (Long-term Analysis, Part 1C-1)
- Solicited Safety Set (except long-term analysis)
- Safety Set
  - When applicable, First Injection Safety Set and Second Injection Safety Set (Part 3 only)

The percentage will be based on subjects in that vaccination group within the Full Analysis Set for each part separately, except the Solicited Safety Set and Safety Set for which the percentages will be based on the vaccination group in the Safety Set (as treated) for each part separately.

For Part 1C-2, Part 2 and Part 3, the number of subjects in the following categories will be summarized based on subjects screened:

- Number of subjects screened
- Number and percentage of screen failure subjects and the reason for screen failure

The percentage of subjects who screen failed will be based on the number of subjects screened. The reason for screen failure will be based on the number of subjects who screen failed.

For long-term analysis, the number and percentage of subjects in each of the following disposition categories will be summarized by vaccination group based on the Randomization Set in Part 1A:

- Received first injection in Part 1A
- Received second injection in Part 1A
- Continuing and unblinded in open-label Part 1B
- Received cross-over first injection in Part 1B

- Received cross-over second injection in Part 1B
- Prematurely discontinued study vaccine during Part 1B and the reason for discontinuation
- Received booster dose in Part 1C-1
- Completed study
- Prematurely discontinued the study and the reason for discontinuation (for the entire study period, and for study parts in applicable subjects cohort)

For Part 1C-1 and Part 1C-2 analyses, the number and percentage of subjects in each of the following disposition categories will be summarized by vaccination group based on the Full Analysis Set for Part 1C-1 or Part 1C-2, respectively:

- Received booster dose
- Completed study

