- Prematurely discontinued the study and the reason for discontinuation

For Part 2 and Part 3 analysis, the number and percentage of subjects in each of the following disposition categories will be summarized by vaccination group based on the Full Analysis Set for each part separately:

- Received each dose of IP
- Prematurely discontinued before receiving the second dose of IP and the reason for discontinuation
- Completed study
- Prematurely discontinued the study and the reason for discontinuation (for the entire study period, and for study parts in applicable subjects cohort)

A subject disposition listing will be provided, including informed consent, subjects who completed the study injection schedule (Long-term analysis, Part 2 and Part 3), subjects who completed study, subjects who discontinued from study vaccine (Long-term analysis, Part 2 and Part 3) or who discontinued from participation in the study, with reasons for discontinuation for each part separately. A separate listing will be provided for screen failure subjects with reasons for screen failure in Part 1C-2, Part 2 and Part 3.

A participant is considered to have completed the study if the participant has completed all periods of the study including the last visit or the last scheduled procedure, as shown in the SoA of each part.

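### Two rules for the same completed-study row: the Part 1A rule cannot count a placebo crossover who declines the booster as a completer, even with full attendance

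*SAP*

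**What the plan says.** The SAP for Part 1A, Section 6.2.1 (Subject Disposition), includes a completed-study row by vaccination group on the Randomization Set. It fixes the meaning as follows: "A subject who completed 12 months of follow up after the last injection received is considered to have completed the study". The sentence does not say whether an open-label injection in Part 1B counts as the last one received.

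The SAP for Parts 1B, 1C, 2 and 3, Section 6.2.1, also has a completed-study row in its long-term disposition table, "summarized by vaccination group based on the Randomization Set in Part 1A". Its rule is different: "A participant is considered to have completed the study if the participant has completed all periods of the study including the last visit" or the final planned procedure, as laid out in the schedule for each part.

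Appendix F of the Part 1A SAP (Section 9.6) gives the schedule for placebo participants who cross over. Its footnote 9 says "OL-D178 is only for those who decline BD". The table has a study-completion row for Part 1B, and its row headed "Days Since Most Recent Injection" shows 149 at OL-D178.

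**The concern.** The same randomized participants, the same denominator and the same row label fall under two rules. One counts elapsed time from an injection; the other counts attendance through the planned schedule. The two agree only where the schedule runs a year past the injection in question. For a placebo participant who crosses over and then declines the booster, it does not: the plan itself ends follow-up about five months after the second open-label dose.

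At stake is the disposition table and listing. Only the placebo arm crosses over, so any shortfall created by the rule falls on that arm. The Part 1A SAP lists premature discontinuation as a separate row with its own reasons, so a full attender who misses the 12-month rule appears in neither row. A reader could take the gap for differential loss to follow-up. The long-term disposition table on the same set could show a different completion figure for the same people.

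**Working it through.** **Inputs**
- Part 1A schedule (Appendix E): second dose at Day 29, last visit at Day 394.
- Part 1B schedule (Appendix F): OL-D1 at about Day 209, window -56/+56 days; second open-label dose at OL-D29, window -3/+7; OL-D178, window ±14.
- Months are days divided by 30.4375.

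**Step 1: reproduce the plan's own figure.** OL-D178 minus OL-D29 = 178 - 29 = 149 days, which matches the schedule. 149 / 30.4375 = 4.9 months.

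**Step 2: apply the visit windows.**
- Shortest: (178 - 14) - (29 + 7) = 164 - 36 = 128 days.
- Longest: (178 + 14) - (29 - 3) = 192 - 26 = 166 days.

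No permitted combination comes near 12 months. Against 365 days, the nominal shortfall is 365 - 149 = 216 days.

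**Step 3: compare with an mRNA-1273 recipient who takes no booster.** 394 - 29 = 365 days. This participant meets the Part 1A rule by attending the planned visits.

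**Step 4: try the other reading, counting from the last Part 1A dose at Day 29.** OL-D178 falls 177 days after OL-D1.

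| Crossover (OL-D1) | OL-D178 falls on | Days after Day 29 | Months |
|---|---|---|---|
| Day 153 (209 - 56) | Day 330 | 301 | 9.9 |
| Day 209 (nominal) | Day 386 | 357 | 11.7 |
| Day 265 (209 + 56) | Day 442 | 413 | 13.6 |

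Adding the ±14 days at OL-D178 widens the range to 287 to 427 days. The participant reaches 365 days when OL-D1 is on Day 217 or later: 217 + 177 = 394, and 394 - 29 = 365.

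**Step 5: classify one full attender (crossed over, no booster, attended OL-D178).**

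| Rule | Completed? |
|---|---|
| Part 1A SAP, any injection received | No, always |
| Part 1A SAP, last Part 1A injection | Depends on the crossover date |
| SAP for the other parts | Yes, always |

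**Step 6: effect on the percentage.** With about 1,000 placebo participants planned, each one misclassified lowers the placebo completion rate by 1/1,000 = 0.1 percentage point. The documents do not say how many are on this pathway.

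**The case against.** The strongest defence is scope. Section 1 limits the Part 1A SAP to the blinded phase unless stated otherwise. Section 6.1 uses last injection to start a follow-up period that ends no later than the first Part 1B injection, so there it means the last Part 1A dose. Crossover disposition also has its own table and rule in the other SAP. On that reading the 149-day comparison falls away. The nominal 357 days (11.7 months) is close to 12 months, and Section 4.1.1 itself describes those who decline a booster as having about 14 months on study, 12 of them follow-up.

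Much of this stands. The 149-day result depends on the literal reading, and on the alternative only crossovers well before Day 217 fall clearly short. It does not rescue the sentence, which neither names the Part 1A dose nor confines completion to the blinded phase. On the alternative reading, two participants with identical attendance can still be classified differently because they crossed over on different dates.

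A reader might also infer that booster recipients fail the rule, since BD-D361 is 360 days after the booster against 365 in Part 1A. The documents do not support that. The rule says 12 months, not 365 days, and the exploratory endpoints for Part 1C-1 (Section 3.2.4 of the other SAP) treat BD-Day 361 as one year after the booster. Boosted crossovers therefore meet the rule in the plan's own terms.

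**Conclusion.** The inconsistency is real and confined to placebo crossovers who decline the booster. Read literally, the Part 1A rule can never classify a full attender on that pathway as a completer (149 days, 128 to 166 with windows). If the last Part 1A dose is meant, the answer turns on crossover timing (301 to 413 days, assuming the second Part 1A dose at Day 29 and OL-D178 on its nominal day). The SAP for the other parts counts the same person as completed in every case.

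The direction is an understated completion percentage in the placebo arm and a possible mismatch with the long-term table. The total size cannot be stated, because the documents give no count of crossovers who decline the booster. A reader might infer a large apparent retention gap of so many points, but any such figure would rest on an assumed share. Nor would these participants be reported as dropouts, since the premature-discontinuation row is defined separately. No endpoint, analysis set or hypothesis test is affected. This is a minor correction to a descriptive table and listing.

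**What to change.** Replace the sentence in Section 6.2.1 of the Part 1A SAP with the rule already used in the SAP for Parts 1B, 1C, 2 and 3. A participant has completed the study if they attended the last visit or last scheduled procedure in the schedule of assessments that applies to them: Day 394, OL-D178 or BD-D361. If the 12-month wording is kept, state which injection it counts from and explain how the row relates to the long-term disposition table.

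The cost is one sentence and a matching change to the derivation of the completion flag for the table and listing. It needs no new data and changes no dose, visit or clinical rule.

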### **6.2.2. Demographics**

Descriptive statistics will be calculated for the following continuous demographic and baseline characteristics: age (years), weight (kg, z-score), height (cm, z-score), and body mass index (BMI) (kg/m^2, z-score). Number and percentage of subjects will be provided for categorical variables such as gender, race, ethnicity. The summaries will be presented by vaccination group as defined in [Section 6.1](#) based on the FAS, Safety Set, Immunogenicity Subset, mITT Set, mITT1 Set, Per-protocol (PP) Immunogenicity Subset and Per-protocol (PP) Efficacy Set. If the Safety Set differs from the Randomization Set (e.g., subjects randomized but not received any study injection; subjects received study vaccination other than the vaccination group they were randomized to), the analysis will also be conducted using the Randomization Set.

For screened failure subjects, age (years), as well as gender, race, ethnicity will be presented in a listing.

In addition, subjects with any inclusion and exclusion criteria violation will also be provided in a listing.

### **6.2.3. Medical History**

Medical history data will be coded by system organ class (SOC) and preferred term (PT) using the Medical Dictionary for Regulatory Activities (MedDRA).

The number and percentage of participants with any medical history and selected medical history conditions will be summarized by SOC and PT based on the Safety Set. A participant will be counted only once for multiple events within each SOC and PT. SOC will be displayed in internationally agreed order. PT will be displayed in descending order of frequency of mRNA-1273 and then alphabetically within SOC.

Medical history data will be presented in a listing.

### **6.2.4. Prior and Concomitant Medications**

Prior and concomitant medications and non-study vaccination will be coded using the World Health Organization (WHO) drug dictionary (WHODD). The summary of concomitant medications will be based on the Safety Set. Categorization of prior, concomitant, and post medications is summarized in [Appendix C Table 7](#).

The number and percentage of subjects using concomitant medications and non-study vaccination during the 7-day follow-up period (i.e., on the day of injection and the 6 subsequent days) and during the 28-day follow-up period after each injection (i.e., on the day of injection and the 27 subsequent days) will be summarized by vaccination groups as defined in [Section 6.1](#) as follows:

- Any concomitant medications and non-study vaccination within 7 Days Post Injection
- Any concomitant medications and non-study vaccination within 28 Days Post Injection
- Seasonal influenza vaccine within 28 Days Post Injection
- Antipyretic or analgesic medication within 28 Days Post Injection

A summary table of concomitant medications and non-study vaccination that continued or newly received at or after the first injection through 28 days after the last injection will be provided by PT in descending frequency in the mRNA-1273 group.

Medications taken to prevent pain or fever will be collected on eDiary and summaries will be provided based on the Solicited Safety Set by vaccination group as defined in [Section 6.1](#) for each injection (first or second) and any injection, including within 7 days after injection, beyond 7 days after injection and after injection.

Prior, concomitant and post medications and non-study vaccination will be presented in a listing.

Concomitant Procedures will be presented in a listing.

#### **6.2.5. Study Exposure**

Study IP administration data will be presented in a listing.

Study duration will be summarized since randomization, since the first injection, and since the second injection.

#### **6.2.6. Major Protocol Deviations**

Major protocol deviations are a subset of protocol deviations that may significantly impact the completeness, accuracy, or reliability of the study data or that may significantly affect a subject's rights, safety, or well-being. Major protocol deviations rules are developed based on the protocol and ongoing data and will be finalized before database lock.

The number and percentage of the subjects with each major protocol deviation type will be provided by vaccination group as defined in [Section 6.1](#) based on the Randomization Set.

Major protocol deviations will be presented in a listing.

### **6.2.7. COVID-19 Impact**

A listing will be provided for COVID-19 impact.

## **6.3. Safety Analysis**

Safety and reactogenicity will be assessed by clinical review of all relevant parameters including solicited ARs (local and systemic), unsolicited AEs, SAEs, MAAEs, AESI, AEs leading to withdrawal from study vaccine and/or study participation, vital signs, and physical examination findings. Unsolicited AEs will be coded by SOC and PT according to the MedDRA. The Toxicity Grading Scale for Healthy Adult and Adolescent Volunteers Enrolled in Preventative Vaccine Clinical Trials (DHHS 2007) is used in this study for solicited ARs as presented in [Table 6 from protocol](#).

All safety analyses will be based on the Safety Set, except summaries of solicited ARs which will be based on the Solicited Safety Set. All safety analyses will be provided by vaccination group unless otherwise specified.

### **6.3.1. Adverse Events**

A treatment-emergent AE (TEAE) is defined as any event occurring during the study not before exposure to study vaccine or any event already present that worsens after exposure to study vaccine. [Note: worsening of a pre-existing condition after vaccination will be reported as a new AE.]

Adverse events will also be evaluated by the investigator for the coexistence of MAAE which is defined as an AE that leads to an unscheduled visit to a healthcare practitioner.

Unsolicited AEs will be coded by PT and SOC using MedDRA and summarized by vaccination group, and stage (up to 28 days after any vaccination and overall stage; see [Section 6.1](#) for definitions of vaccination group and stage).

All summary tables (except for the overall summary of AEs) for unsolicited AEs will be presented by SOC and PT for TEAEs with numbers of subjects included. SOC will be displayed in internationally agreed order. PT will be displayed in descending order of frequency of mRNA-1273 and then alphabetically within SOC. When summarizing the

number and percentage of subjects with an event, subjects with multiple occurrences of the same AE or a continuing AE will be counted once. Subjects will be presented according to the highest severity (the strongest relationship) in the summaries by severity (of related AEs), if subjects reported multiple events under the same SOC and/or PT.

Percentages will be based upon the number of subjects in the Safety Set within each vaccination group.

